Clinical Protocol Synopsis: Study I4V-CR-JAGS(b)

Name of Investigational Product: Baricitinib (LY3009104)	
Title of Study: A Randomized, Double-Blind, Placebo- Controlled, Phase 3 Study Evaluating the Efficacy and Safety of Baricitinib in Patients with Moderately to Severely Active Rheumatoid Arthritis Who Have Had an Inadequate Response to Methotrexate Therapy	
Number of Planned Patients: Entered: 411 Enrolled/Randomized: 288 (144 on baricitinib, 144 on placebo) Completed: Approximately 245	Phase of Development: 3
Length of Study: 2 years Planned first patient visit: Jun 2014 Planned last patient visit: Jun 2016	

Objectives: The primary objective of the study is to determine whether baricitinib is superior to placebo in the treatment of patients with moderately to severely active rheumatoid arthritis (RA) despite methotrexate treatment (that is, inadequate response to methotrexate [MTX-IR]), as assessed by the proportion of patients achieving a 20% improvement in American College of Rheumatology criteria (ACR20) at Week 12.
 
The secondary objectives of the study are to evaluate the efficacy of baricitinib versus placebo as assessed by:
 
 • change from baseline to Week 12 in Health Assessment Questionnaire-Disability Index (HAQ-DI) score compared to placebo • change from baseline to Week 12 in Disease Activity Score modified to include the 28 diarthroidal joint count (DAS28)-high-sensitivity C-reactive protein (hsCRP) compared to placebo • proportion of patients achieving a Simplified Disease Activity Index (SDAI) score ≤ 3.3 at Week 12 compared to placebo • mean duration of morning joint stiffness in the 7 days prior to Week 12 compared to placebo as collected in diaries • mean severity of morning joint stiffness in the 7 days prior to Week 12 compared to placebo as collected in diaries • mean Worst Tiredness numeric rating scale (NRS) in the 7 days prior to Week 12 compared to placebo as collected in diaries • mean Worst Joint Pain NRS in the 7 days prior to Week 12-compared to placebo as collected in diaries 
The exploratory objectives in the study include:
 
 • change from baseline at Weeks 16, 24 and 52 in structural joint damage as measured by modified Total Sharp Score (mTSS; van der Heijde 2000) • proportion of patients with mTSS change ≤ 0 from baseline at Weeks 16, 24, and 52 • change from baseline to Weeks 16, 24, and 52 in joint space narrowing and bone erosion scores • proportion of patients achieving DAS28-hsCRP ≤ 3.2 and DAS28-hsCRP < 2.6 at Weeks 12, 24, and 52 • proportion of patients achieving HAQ-DI improvement ≥ 0.22 and ≥ 0.3 at Weeks 12, 24, and 52 • proportion of patients achieving ACR20 at Week 24 and Week 52 • proportion of patients achieving 50% improvement in American College of Rheumatology criteria (ACR50) at Weeks 12, 24, and 52 • proportion of patients achieving 70% improvement in American College of Rheumatology criteria (ACR70) at Weeks 12, 24, and 52 • percentage change from baseline to Weeks 12, 24, and 52 in individual components of the ACR Core Set • change from baseline through Week 52 in DAS28-hsCRP • change from baseline through Week 52 in DAS28-erythrocyte sedimentation rate (ESR) • proportion of patients achieving DAS28-ESR ≤ 3.2 and DAS28-ESR < 2.6 at Weeks 12, 24, and 52 • change from baseline to Week 24 and Week 52 in HAQ-DI score • change from baseline to Weeks 12, 24, and 52 in Clinical Disease Activity Index (CDAI) score 	

- change from baseline to Weeks 12, 24, and 52 in SDAI score
- proportion of patients achieving a CDAI score ≤ 2.8 at Weeks 12, 24, and 52
- proportion of patients achieving an SDAI score ≤ 3.3 , Week 24, and Week 52
- proportion of patients achieving ACR/European League Against Rheumatism (EULAR) remission according to the Boolean-based definition at Weeks 12, 24, and 52
- proportion of patients achieving moderate and good EULAR responses based on the DAS28 at Weeks 12, 24, and 52
- evaluation of hybrid ACR (bounded) response at Weeks 12, 24 and 52
- change from baseline to Weeks 12, 24, and 52 in Functional Assessment of Chronic Illness Therapy Fatigue (FACIT-F) scale scores
- change from baseline to Weeks 12, 24 and 52 in European Quality of Life-5 Dimensions-5 Level (EQ-5D-5L) scores
- change from baseline to Weeks 12, 24 and 52 in Work Productivity and Activity Impairment-Rheumatoid Arthritis (WPAI-RA) scores
- evaluation of healthcare resource utilization through Week 52
- change from baseline to Weeks 12, 24 and 52 in duration of morning joint stiffness assessed at the visit using an electronic patient-reported outcomes (ePRO) tablet
- change from baseline to Weeks 12, 24 and 52 in Worst Tiredness NRS assessed at the visit using an ePRO tablet
- change from baseline to Weeks 12, 24 and 52 in Worst Joint Pain NRS assessed at the visit using an ePRO tablet.

Study Design: Study I4V-CR-JAGS(b) (JAGS) will be a 52-week, Phase 3, multicenter, randomized, double-blind, placebo- controlled, parallel-group, study comparing the efficacy of baricitinib versus placebo in patients with moderately to severely active RA who have had an insufficient response to MTX and who have never been treated with a biologic disease-modifying antirheumatic drug (DMARD) (that is, MTX-IR patients). Baricitinib will be administered as a 4-mg tablet QD. The dose for patients with renal impairment, defined as estimated glomerular filtration rate (eGFR) < 60 mL/min/1.73 m², will be 2 mg baricitinib QD. Patients not assigned to the baricitinib treatment arm will receive either a 4-mg or 2-mg matching placebo tablet.

A total of 288 patients are planned for enrollment in this study (144 to receive baricitinib, and 144 to receive placebo). After the Week 52 study visit, eligible patients may proceed to a separate extension study (Study I4V-MC-JADY [JADY]) lasting for up to 2 years or to the posttreatment follow-up period of this study (Part C).

Study JAGS will consist of 4 parts:

- Screening: Screening period lasting from 3 to 42 days prior to Visit 2 (Week 0)
- Part A: double-blind, placebo-controlled period from Week 0 through Week 24
- Part B: open-label period from Week 24 through Week 52
- Part C: posttreatment follow-up period.

Diagnosis and Main Criteria for Inclusion and Exclusions: The proposed patient population for Study I4V-CR-JAGS(b) (JAGS) will be ambulatory adult patients with moderately to severely active RA who have had an insufficient response to MTX and who have never been treated with a biologic DMARD. Patients will be eligible for participation only if they have an inadequate response to MTX as evidenced by the presence of at least 6/68 tender joints and 6/66 swollen joints and an hsCRP measurement ≥ 6 mg/L.

Investigational Product, Dosage, and Mode of Administration or Intervention:

Baricitinib 4 mg administered orally QD

Planned Duration of Treatment: 52 weeks.

Screening period: 3 to 42 days

Treatment period: 52 weeks

Follow-up period: 28 days

Reference Therapy, Dose, and Mode of Administration or Comparative Intervention:

Placebo tablets matching baricitinib will be administered orally QD.

Patients will continue to take their background MTX therapy during the course of the study.

Criteria for Evaluation:

Efficacy

The following efficacy measures will be assessed in this study:

- ACR20, ACR50, and ACR70 indices
- HAQ-DI
- DAS28-hsCRP and DAS28-ESR
- Hybrid ACR (bounded) response measure
- SDAI
- CDAI
- EULAR responses based on DAS28
- mTSS (includes joint space narrowing score and bone erosion score)

Health Outcomes

The following health outcome measures will be administered in this study:

- duration and severity of morning joint stiffness
- recurrence of joint stiffness during the day
- tiredness severity numeric rating scale (Worst Tiredness NRS)
- pain severity numeric rating scale (Worst Joint Pain NRS)
- FACIT-F
- WPAI-RA
- EQ-5D-5L
- Quick Inventory of Depressive Symptomatology Self-Rated-16 (QIDS-SR₁₆)
- healthcare resource utilization

Safety

The following safety measures will be assessed in this study:

- adverse events (AEs)
- adverse events of special interest (AESIs)
- serious adverse events (SAEs)
- suspected unexpected serious adverse reactions (SUSARs)

- physical examinations
- electrocardiograms (ECGs)
- chest x-ray and tuberculosis (TB) testing
- vital signs (blood pressure and heart rate) and physical characteristics
- standard laboratory tests (including hematology, clinical chemistry, urinalysis, lipid profile, eGFR, iron studies, hsCRP, and ESR)
- concomitant medications

AESIs will include:

- severe or opportunistic infections
- myelosuppressive events of anemia, leukopenia, neutropenia, lymphopenia, and thrombocytopenia
- thrombocytosis
- elevations in alanine aminotransferase (ALT) or aspartate aminotransferase (AST) (>3 times ULN) with total bilirubin (>2 times ULN)

Patients with these laboratory value specified events will be identified using the same criteria for the interruption of investigational product with the exception of anemia, which will be identified using the same criteria for the discontinuation of investigational product, and thrombocytosis, which will be defined as a platelet count >600,000/ μ L.

Pharmacogenetics

Samples will be stored, and analysis may be performed on genetic variants thought to play a role in active RA and the JAK/signal transducers and activators of transcription (STAT) signaling pathways.

Statistical Methods:

Stratification:

Randomization will be stratified at the country level and joint erosion status (1-2 joint erosions plus seropositivity versus at least 3 joint erosions)

Sample size:

288 patients (144 in baricitinib, 144 in placebo) will provide:

- 99% power to detect a difference between the baricitinib and placebo treatment groups in ACR20 response rate (60% versus 35%) at Week 12 based on a 2-sided chi-square test at a significance level of 0.05.

The above sample size and power estimates are based on nQuery advisor 7.0.

General considerations:

All statistical tests of treatment effects will be performed at 2-sided significance levels of 0.05, unless otherwise stated. Treatment comparisons of discrete efficacy variables will be made using a logistic regression analysis with country, treatment groups and joint erosion status in the model. The proportions and 95% confidence interval (CI) will be reported. Treatment comparisons of continuous efficacy variables will be made using analysis of covariance (ANCOVA) with country, treatment groups, joint erosion status and baseline value in the model. Type III sums of squares for the least-squares (LS) means will be used for the statistical comparison; the 95% CI will also be reported.

When a restricted maximum likelihood (REML)-based mixed model for repeated measures (MMRM) is used, the model will include the fixed, categorical effects of treatment, country, joint erosion status, visit, treatment-by-visit-interaction, as well as the continuous, fixed covariates of baseline score and baseline score-by-visit-interaction. An unstructured (co)variance structure will be used to model the within-patient errors. If this analysis fails to converge, other structures will be tested. Type III sums of squares for the LS means will be used for the statistical comparison; the 95% CI will also be reported. Treatment group comparisons with placebo at Week 12 and all other visits will be tested. Further details on the MMRM will be described in the statistical analysis plan (SAP).

Fisher's exact test will be used for all AEs, discontinuation, and other categorical safety variables. Continuous vital

signs and other continuous safety variables including laboratory parameters will be analyzed by using ANCOVA with treatment and baseline value in the model.

Analysis population:

Unless otherwise specified, the efficacy and safety analyses will be conducted on a modified intent-to-treat basis (Gillings and Koch 1991). This analysis set includes all data from all randomized patients who received at least 1 dose of study drug. Patients will be analyzed according to the treatment to which they were assigned.

Sensitivity analyses of the primary endpoints may be conducted and will be described in the statistical analysis plan.

Missing data imputation:

In accordance with precedent set with other Phase 3 RA trials (Cohen et al. 2006; Keystone et al. 2004, 2008, 2009; Smolen et al. 2008, 2009), the following methods for imputation of missing data will be used:

- Nonresponder imputation (NRI): All patients who discontinue the study or the study treatment at any time for any reason will be defined as nonresponders for the NRI analysis for categorical variables, such as ACR20/50/70, from the time of discontinuation and onward. Patients who receive rescue therapy at Week 16 will be analyzed as nonresponders after Week 16 and onward. Randomized patients without available data at a postbaseline visit will be defined as nonresponders for the NRI analysis at that visit.
- Linear extrapolation method: The linear extrapolation method will be used for analysis of the structural progression endpoint (van der Heijde mTSS) to impute missing data at time points when analyses are conducted (including the analyses at Week 24 and Week 52). For patients who discontinue the study or the study treatment or for patients who miss a radiograph for any reason, baseline data and the most recent radiographic data prior to discontinuation or the missed radiograph, adjusted for time, will be used for linear extrapolation to impute missing data at subsequent time points. For patients who receive rescue therapy starting at Week 16 or at any time point thereafter, baseline data and the most recent radiographic data prior to initiation of rescue therapy, adjusted for time, will be used for linear extrapolation. All patients originally randomized to placebo will be switched to active treatment at Week 24; thus, there will be no observed data for the placebo arm for the structural comparison at subsequent time points. Therefore, baseline data and the most recent radiographic data prior to initiation of the new therapy, adjusted for time, will be used for linear extrapolation at Week 52. The linear extrapolation method has been established as an appropriate missing data imputation method in other Phase 3 RA trials (Keystone et al. 2004, 2008, 2009; Cohen et al. 2006; Smolen et al. 2008, 2009). Missing postbaseline values will be imputed only if both a baseline value and a postbaseline value from another time point are available, as long as the patient was on the same treatment at each applicable time point.
- Multiple imputation: Other methods than linear extrapolation that include multiple imputation will be employed for analysis of the structural progression endpoint (van der Heijde mTSS) to impute missing data at Week 24. Details will be provided in the SAP.
- Modified baseline observation carried forward (mBOCF): The mBOCF method will be used for the analysis of secondary continuous endpoints (unless otherwise stated). For patients who discontinue the study or the study treatment because of an AE, including death, the baseline observation will be carried forward to the corresponding endpoint for evaluation. For patients who discontinue the study for reason(s) other than an AE, the last nonmissing postbaseline observation prior to discontinuation will be carried forward to the corresponding endpoint for evaluation. For patients who receive rescue therapy starting at Week 16, the last nonmissing observation at or before rescue will be carried forward to subsequent time points for evaluation.
- Modified last observation carried forward (mLOCF): For all continuous measures including safety analyses, the mLOCF will be a general approach to impute missing data unless otherwise specified. For patients who receive rescue therapy starting at Week 16, the last nonmissing observation at or before rescue will be carried

forward to subsequent time points for evaluation. For all other patients discontinuing from the study or the study treatment for any reason, the last nonmissing postbaseline observation before discontinuation will be carried forward to subsequent time points for evaluation. After mLOCF imputation, data from patients with nonmissing baseline and postbaseline observations will be included in the analyses. The mLOCF will be used as a sensitivity method to the mBOCF method with respect to the secondary endpoints.

- Other methods for data imputation for analysis of endpoints other than mTSS may be used and will be described in the SAP.

Analyses methods:

Primary analysis:

A logistic regression model with treatment, country and joint erosion status in the model will be used to test the treatment difference between baricitinib and placebo in the proportion of patients achieving ACR20 response at Week 12. The NRI method as described above will be used to impute missing data.

Secondary analyses:

- Comparison between baricitinib and placebo in change from baseline to Week 12 in HAQ-DI score: An ANCOVA analysis with treatment, country, joint erosion status and baseline score in the model will be used to test the treatment difference between baricitinib and placebo in change from baseline to Week 12 in HAQ-DI. The mBOCF and mLOCF approaches as described above will be used to impute missing data.
- Comparison between baricitinib and placebo in change from baseline to Week 12 in DAS28-hsCRP: An ANCOVA model with treatment, country, joint erosion status, and baseline score in the model will be used to test the treatment difference between baricitinib and placebo in change from baseline to Week 12 in DAS28-hsCRP. The mBOCF and mLOCF approaches as described above will be used to impute missing data.
- Comparison between baricitinib and placebo in proportion of patients achieving an SDAI score ≤ 3.3 at Week 12: A logistic regression model with treatment, country, and joint erosion status in the model will be used to test the treatment difference between baricitinib and placebo in the proportion of patients achieving an SDAI score ≤ 3.3 response at Week 12. The NRI method as described above will be used to impute missing data.
- Comparison between baricitinib and placebo in mean duration of morning stiffness in the 7 days prior to Week 12: An ANCOVA analysis with treatment, country, joint erosion status and baseline score (Day 1 on the diaries) in the model will be used to test the treatment difference between baricitinib and placebo in mean duration of morning stiffness.
- Comparison between baricitinib and placebo in mean severity of morning joint stiffness in the 7 days prior to Week 12: An ANCOVA analysis with treatment, country, joint erosion status and baseline score (Day 1 on the diaries) in the model will be used to test the treatment difference between baricitinib and placebo in mean severity of morning joint stiffness.
- Comparison between baricitinib and placebo in mean “Worst Tiredness” NRS in the 7 days prior to Week 12: An ANCOVA model with treatment, country, joint erosion status, and baseline score (Day 1 on the diaries) in the model will be used to test the treatment difference between baricitinib and placebo in mean “Worst Tiredness” NRS.
- Comparison between baricitinib and placebo in mean “Worst Joint Pain” NRS in the 7 days prior to Week 12: An ANCOVA model with treatment, country, joint erosion status, and baseline score (Day 1 on the diaries) in the model will be used to test the treatment difference between baricitinib and placebo in mean “Worst Joint Pain” NRS.

Besides the analyses listed in the objective section, the following analyses will be performed as well.

- change from baseline in mTSS
- proportion of patients with mTSS change ≤ 0
- change from baseline in joint space narrowing and bone erosion scores
- proportion of patients achieving DAS28-hsCRP ≤ 3.2 and < 2.6

- proportion of patients achieving HAQ-DI improvement ≥ 0.22 and ≥ 0.3
- proportions of patients achieving ACR20 (other than primary), ACR50, and ACR70
- percentage change from baseline in individual components of the ACR Core Set
- change from baseline in DAS28-hsCRP
- change from baseline in DAS28-ESR
- proportion of patients achieving DAS28-ESR ≤ 3.2 and < 2.6
- change from baseline in HAQ-DI
- change from baseline in CDAI score
- change from baseline in SDAI score
- proportion of patients achieving CDAI score ≤ 2.8
- proportion of patients achieving SDAI score ≤ 3.3 (ACR/EULAR remission according to the Index-based definition)
- proportion of patients achieving ACR/EULAR remission according to the Boolean-based definition
- proportion of patients achieving moderate response and good response based on EULAR response criteria
- hybrid ACR (bounded) response measure
- change from baseline in fatigue score in the FACIT-F
- change from baseline in health states, VAS score, and index score of EQ-5D-5L
- change from baseline in absenteeism, presenteeism, work productivity loss, and activity impairment scores of WPAI-RA
- individual items and total score in healthcare resource utilization
- change from baseline in duration of morning joint stiffness assessed at the visit using an ePRO tablet
- change from baseline in Worst Tiredness NRS assessed at the visit using an ePRO tablet
- change from baseline in Worst Joint Pain NRS assessed at the visit using an ePRO tablet.

Approaches similar to the primary and above secondary analyses will be used to analyze other exploratory and health outcome measures. Analysis methods will consist of ANCOVA and logistic regression, as described above, using mBOCF, linear extrapolation, NRI, and mLOCF missing data imputation methods, as applicable.

In addition, continuous parameters that are collected at repeated visits throughout the double-blind period may be analyzed using a MMRM approach as described in the general consideration section.

Safety:

All safety data will be descriptively summarized by treatment groups and analyzed using the mITT population. For the purposes of calculating changes from baseline during Part A and Part B treatment, baseline may be considered as the original baseline for Part A – prior to any study drug received – or at the visits that mark the transition between treatments received, depending on the purpose of the summary or comparison being made. Summaries within Parts A and B will be conducted by treatment group used within each respective part. Additional summaries by treatment group that continue unchanged across multiple parts of the study will be conducted, as appropriate.

Treatment-emergent adverse events are defined as AEs that first occurred or worsened in severity after the first dose of study treatment. AEs will be considered treatment emergent for nonresponders assigned to baricitinib if the AEs first occurred or worsened in severity after the visit at which rescue therapy is assigned. The number of TEAEs as well as the number and percentage of patients who experienced at least 1 TEAE will be summarized using Medical Dictionary for Regulatory Activities (MedDRA) for each system organ class (SOC) (or a body system) and each preferred term by treatment group. TEAEs will also be summarized by relationship to treatment and by severity within each treatment group. Serious adverse events (SAEs) and AEs that lead to study drug discontinuation will also be summarized by treatment group. Fisher's exact test will be used to perform the

statistical comparisons between baricitinib and placebo.

All clinical laboratory results will be descriptively summarized by treatment group. Individual results that are outside of normal range will be flagged in data listings. Quantitative clinical hematology, chemistry, and urinalysis variables obtained at the baseline to postbaseline visits will be summarized as changes from baseline by treatment group and analyzed using ANCOVA with treatment and baseline value in the model. Categorical variables, including the incidence of abnormal values and incidence of AESIs, will be summarized by frequency and percentage of patients in corresponding categories. Shift tables will be presented for selected measures. Observed values and changes from baseline (predose or screening if missing) for vital signs and physical characteristics will be descriptively summarized by treatment group and time point. Change from baseline to postbaseline in vital signs, QIDS-SR16, and body weight will be analyzed using ANCOVA with treatment and baseline value in the model.

The incidence and average duration of study drug interruptions will be summarized and compared descriptively among treatment groups. Various techniques may be used to estimate the effects of study drug interruptions on safety measures. Further analyses may be performed and will be planned in the SAP.

Data collected after initiation of rescue therapy will be summarized as appropriate.

3. Table of Contents

A Randomized, Double-Blind, Placebo- Controlled, Phase 3 Study Evaluating the Efficacy and Safety of Baricitinib in Patients with Moderately to Severely Active Rheumatoid Arthritis Who Have Had an Inadequate Response to Methotrexate Therapy

Section	Page
1. Protocol I4V-CR-JAGS(c) A Randomized, Double-Blind, Placebo-Controlled, Phase 3 Study Evaluating the Efficacy and Safety of Baricitinib in Patients with Moderately to Severely Active Rheumatoid Arthritis Who Have Had an Inadequate Response to Methotrexate Therapy	1
2. Synopsis	2
3. Table of Contents.....	11
4. Abbreviations and Definitions.....	18
5. Introduction	24
6. Objectives.....	27
6.1. Primary Objective	27
6.2. Secondary Objectives.....	27
6.3. Exploratory Objective	27
7. Investigational Plan.....	29
7.1. Summary of Study Design.....	29
7.1.1. Screening Period	30
7.1.2. Part A and Part B: 24-Week Double-Blind Placebo-Controlled, (Part A) Period and 28-Week Open-Label (Part B) Period.....	30
7.1.3. Part C: Posttreatment Follow-Up Period.....	31
7.1.4. Study Extensions.....	31

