12.1. Determination of Sample Size

Approximately 288 patients (144 in baricitinib, 144 in placebo) will provide:

- 99% power to detect a difference between the baricitinib and placebo treatment groups in ACR20 response rate (60% versus 35%) at Week 12 based on a 2-sided chi-square test at a significance level of 0.05.

The sample size and power estimates were obtained using nQuery[®] Advisor 7.0.

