6.2. Adjustments for Covariates

The covariates used in the parametric statistical model (ANCOVA) of continuous data generally will include the parameter value at baseline. Inclusion of baseline in the ANCOVA model provides estimated adjusted (least squares) means for each treatment reflecting averages for the average baseline patient. Other independent variables that will be included in the models for efficacy and health outcomes analyses to adjust estimates of treatment effect include the stratifying variables country and joint erosion status. When the patient number in each country is deemed small (ie, $n < 30$), countries will be combined into regions (ie, East Asia and Central America). The independent variables used in the logistic regression models will include country/region and joint erosion status (refer to Section 6.1). The stratification variables used in the analyses will be derived based on electronic case report form (eCRF) data and x-ray data collected by Bioclinica.

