- A logistic regression analysis will be conducted to analyze the patients with specified categories up to Week 24 as below. The model for the logistic regression will consist of country/region, baseline joint erosion status, and treatment as fixed effects to compare baricitinib to placebo. Besides, descriptive statistics will be provided by visit and by treatment group for the following endpoints.
 - The proportion of patients achieving DAS28-ESR ≤ 3.2 and < 2.6 and DAS28-hsCRP ≤ 3.2 and < 2.6 at post-baseline visits.
 - The proportion of patients achieving HAQ-DI improvement from baseline ≥ 0.22 and ≥ 0.3
 - The proportion of patients achieving SDAI score ≤ 3.3 (ACR/EULAR remission index-based definition) and CDAI score ≤ 2.8 up to Week 52; the proportion of patients achieving CDAI score ≤ 10 and proportion of patients achieving SDAI score ≤ 11 up to Week 52.
 - The proportion of patients achieving ACR/EULAR remission according to the Boolean-based definition by treatment group.

- Change from baseline to postbaseline visits up to Week 24 in specific endpoints will be analyzed using an ANCOVA model with treatment, country/region, baseline joint erosion status, and baseline score in the model to test the treatment difference between baricitinib and placebo.
Besides, descriptive statistics will be provided by visit and by treatment group for the following endpoints. The mLOCF approach described in Section 6.3.1 will be used to impute missing data.
 - The percent change from baseline and change from baseline in individual components of the ACR core set, including TJC68, SJC66, patient's assessment of arthritis pain, Patient's Global Assessment of Disease Activity, Physician's Global Assessment of Disease Activity, and hsCRP at postbaseline visits.
 - The actual score and the change in DAS28-hsCRP and in DAS28-ESR from baseline to post-baseline visits.
 - The actual score and the change in HAQ-DI from baseline to post-baseline visits.
 - The actual score and the change in CDAI and in SDAI from baseline to post-baseline.

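### Logistic models for the threshold endpoints omit the baseline score that the ANCOVAs include: the tests are valid but probably less efficient than they could be, with little effect on SDAI remission

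*Protocol*

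**What the plan says.** The protocol synopsis (General considerations) sets the model for all responder endpoints: "Treatment comparisons of discrete efficacy variables will be made using a logistic regression analysis with country, treatment groups and joint erosion status". Protocol 12.2.1 repeats it. For SDAI at or below 3.3 at Week 12, the synopsis and Protocol 12.2.7 compare the arms with the same terms: "A logistic regression model with treatment, country, and joint erosion status in the model will be used to test the treatment difference between baricitinib".

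The SAP agrees. Section 6.2: "The independent variables used in the logistic regression models will include country/region and joint erosion status". Section 6.11.2 uses the same terms for SDAI remission. Section 6.16, covering the DAS28, HAQ-DI, SDAI and CDAI cut-offs and Boolean remission up to Week 24, says: "The model for the logistic regression will consist of country/region, baseline joint erosion status, and treatment as fixed effects".

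By contrast, the ANCOVAs for change from baseline (Protocol 12.2.1; SAP 6.1, 6.11.2, 6.16) include the baseline value, and SAP 6.2 explains why. It gives no reason for leaving the score out once the endpoint is dichotomised. No baseline-adjusted logistic sensitivity model is planned.

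SAP 6.1 also has a sparse-data rule. If any category of any model factor has fewer than five responders, the Fisher exact p-value replaces the logistic odds ratio and its interval.

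**The concern.** These endpoints depend on where the patient starts. SDAI, DAS28, CDAI and Boolean remission require reaching an absolute level, and the HAQ-DI endpoints require a fixed absolute drop. In a logistic model, omitting a prognostic baseline lowers the power to detect a treatment effect. It also forgoes the chance to account for an accidental baseline difference between arms.

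At stake is efficiency for SDAI remission, the only binary endpoint among the seven secondaries, and for a family of exploratory responder comparisons. ACR20 is a relative improvement and is outside this point.

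**Working it through.** **1. The plan's own power figure.** Protocol 12.1 claims "99% power to detect a difference between the baricitinib and placebo treatment groups in ACR20 response rate (60% versus 35%) at Week 12". The test assumed is a chi-square without covariates, two-sided at 0.05. With 144 per arm and mean rate (0.60 + 0.35)/2 = 0.475:

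z = [0.25 − 1.96 × √(2 × 0.475 × 0.525/144)] / √[(0.60 × 0.40 + 0.35 × 0.65)/144] = (0.25 − 0.1153)/0.0570 = 2.36, so power is 99.1%.

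The figure reproduces. It concerns ACR20 only and says nothing about the threshold endpoints.

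**2. Is baseline plausibly prognostic?** The documents suggest so.

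- HAQ-DI moves in steps of 0.125 (SAP Appendix 2), and the entry criteria set no HAQ-DI minimum. A patient starting at 0 or 0.125 cannot improve by 0.22, and one starting at 0.25 or below cannot improve by 0.3, in either arm.
- Eligibility sets floors for joint counts and hsCRP but no ceilings, so distance from the absolute thresholds can vary widely.
- SAP 6.6.2 tabulates a baseline DAS28 category of 3.2 or below. Such a patient already meets one of the endpoints.

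**3. Assumptions for size.** From the documents: 144 per arm, two-sided 0.05. Assumed: response rates, strength of the baseline effect, an 80/20 region split and a 70/30 erosion split. The planned Wald test (treatment, region, erosion) is compared with the same model plus standardised baseline x.

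- Model A: logit P(response) = a(arm) − ln(OR) × x, with OR per SD of 1.5, 2 or 3 and a(arm) set to give the stated rates.
- Model B (absolute level): y = ρx + √(1 − ρ²)e, response if y falls below an arm-specific cut, with ρ = 0.3, 0.45 or 0.6.
- Model C (fixed drop): same y, response if x − y exceeds a cut. The correlation of baseline with the drop is √((1 − ρ)/2), that is 0.59, 0.52 or 0.45.

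**4. Power without → with baseline (%).**

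| Endpoint type, placebo v baricitinib | Model | Three baseline strengths, in the order above |
|---|---|---|
| DAS28/CDAI 10 v 20 | A | 66.7→67.6; 67.1→69.1; 65.4→72.0 |
| DAS28/CDAI 15 v 30 | A | 86.2→87.2; 87.2→90.0; 87.9→92.1 |
| DAS28-type 20 v 35 | B | 81–82 → 83; 86; 90 |
| HAQ-DI 40 v 55 | A | 72.4→73.9; 70.9→75.3; 71.8→80.4 |
| HAQ-DI 45 v 60 | A | 73.6→74.5; 72.5→76.7; 72.3→80.3 |
| HAQ-DI 40 v 55 | C | 72.2→82.4; 72.3→80.0; 73.6→78.2 |
| HAQ-DI 45 v 60 | C | 72.3→82.9; 71.8→79.4; 72.8→78.1 |

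The loss from omission is therefore about 1 to 8 points for DAS28/CDAI and about 1 to 11 for HAQ-DI. With OR per SD = 1 the Model A differences were −0.2 to +0.4 points, which is noise. At 3,000 trials the simulation error is √(0.66 × 0.34/3000) ≈ 0.9 points per estimate.

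**5. SDAI remission with the SAP 6.1 Fisher rule applied (Model B).**

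| Placebo v baricitinib | Fisher used | ρ = 0.3 | 0.45 | 0.6 |
|---|---|---|---|---|
| 6 v 15 | about 33% | 68.0→68.8 | 67.9→70.3 | 69.3→75.0 |
| 3 v 10 | about 86% | 62.6→62.9 | 60.5→61.3 | 61.6→63.0 |
| 2 v 8 | about 97% | 53.5→53.5 | 55.3→55.5 | 53.4→53.6 |

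The largest gap (5.7 points) was rechecked with 12,000 trials: 69.4→74.0, or 4.6 points. Hence about 0 to 5 points. With three regions split 70/15/15, Fisher is used in about 79% of trials even at 6 v 15. Ignoring the rule at 6 v 15 would give 71% against 73, 75 and 78%, which is not the planned procedure.

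**The case against.** The case against acting is substantial.

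- **Nothing is invalid.** Adjusting for the stratification factors is coherent, and protocol and SAP agree. Chance imbalance is already reflected in the test's error rate. A reader might infer that the planned tests are biased or have inflated type I error; nothing in the documents supports that. This stands.
- **The SDAI effect is small.** A reader might infer that the one binary secondary endpoint loses material power. The Fisher rule largely removes that reading, because when remission is rare the reported p-value would usually be the same with or without the covariate. This stands.
- **The size rests on assumptions.** No rates or baseline associations are given, and the loss is zero if baseline is not prognostic. This stands, so the loss should be stated conditionally.
- **Related analyses exist.** Baseline-adjusted ANCOVAs cover the continuous scores, SAP 6.15 plans subgroups by baseline DAS28-hsCRP, and all the threshold endpoints except SDAI at Week 12 are exploratory. This lowers the priority but does not replace adjustment in the responder models.
- **Adding a covariate has side effects.** SAP 6.3.1 allows for missing baselines, and such patients would drop out of the adjusted model although nonresponder imputation otherwise keeps them. Boolean remission has no single baseline index. Both need a rule, given under the fix.

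In the other direction, adding baseline did not lower power beyond simulation noise in any scenario. Type I error with adjustment stayed at 4.4 to 5.5%. A continuous covariate adds no factor category, so it would not trigger the Fisher rule more often.

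**Conclusion.** The omission is real and consistent across both documents. It is an efficiency point, conditional on baseline being prognostic, which is plausible for absolute levels and fixed drops. Under assumed rates and baseline strengths the loss is about 1 to 8 points of power for the DAS28/CDAI cut-offs, about 1 to 11 for the HAQ-DI cut-offs, and about 0 to 5 for SDAI remission, near zero if remission is rare. No size was derived for Boolean remission. The ACR20 primary analysis and its 99% power are unaffected. The documents do not support calling the planned tests invalid, or calling SDAI remission seriously underpowered for this reason.

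**What to change.** Before the single unblinding, amend Protocol 12.2.1 (with the matching synopsis and 12.2.7 wording) and SAP 6.1, 6.2, 6.11.2 and 6.16 as follows.

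- Add the continuous baseline of the same index to each threshold-endpoint logistic model: baseline SDAI for SDAI, DAS28 for the DAS28 cut-offs (same version, hsCRP or ESR), CDAI for CDAI, HAQ-DI for HAQ-DI. For Boolean remission name one covariate, for example baseline SDAI.
- Leave the ACR20 primary model unchanged.
- State that the SAP 6.1 Fisher fallback still applies as written.
- Impute a missing baseline covariate, for example with the overall baseline mean across both arms, so that no mITT patient is lost.

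The cost is low: the components of each index are already scheduled at Visit 2. Protocol 12.2.1 requires an amendment only when a principal feature changes; otherwise the change can be described and justified in the SAP and study report. The one downside is that the odds ratio becomes conditional on baseline as well as on country/region and erosion status. The Newcombe-Wilson risk difference already planned for SDAI, or a standardised risk difference, can be reported beside it.
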